fPER. Our User Testing dialogs provided a number of ideas for new approaches that will be incorporated into **fPER**. User Testing has indicated the time immediately before transplant to be a time of significant distress associated with anticipation and fear of the unknown. Many caregivers felt additional support after day 100 would also be helpful when transplant program support generally declined though they were still dealing with post-transplant issues. To address these issues, **fPER** will begin prior to transplant (unlike the previous study where the first session often did not begin until more than two weeks after the transplant). The active treatment will be increased to 10 manualized sessions (from 8 in **PEPRR**) to include two additional sessions between 4-6 months post-transplant. **fPER** will also include incorporation of Smartphone technology to make the interventionist available by video chat. Thus, **fPER** represents targeted modifications from the initial intervention with many enhancements and improvements that will enhance scheduling flexibility, improve retention and intervention completion rates, as well as improve outcome. Behavioral assessments will be collected prior to randomization, and at 6 weeks, 3 months and 6 months after transplant (anchored to the day of transplant as day 0). Blood samples from caregivers will be collected at the same time whereas hair samples will be collected every three months: baseline (patient and caregiver), 3 (caregiver) and 6 (patient and caregiver) months post-transplant. **fPER** sessions will be delivered either at the clinic during patient visits or via video chat.

Each **fPER** session will be devoted to a separate topic with the goal of assisting the caregiver in the development and application of stress-management coping skills including learning problem-solving skills, identifying cognitive distortions, application of relaxation techniques, use of the emWave2, coping skills training, effective use of social support, and establishing appropriate goals. The intervention meets the needs and requests identified in User Testing. All caregivers in **fPER** will be provided a Caregiver Workbook that includes information about the session topics and homework assignments.

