A possible problem rests in the burden for the caregiver. We have worked hard to minimize the inconvenience to the caregiver in this project to reduce drop outs and maintain compliance. Another issue is related to patient death or subject dropout. For this reason, we use intent to treat design with the last valid measure carried forward. Subject dropouts will be considered to occur completely at random unless otherwise indicated. Caregivers are expected to be generally healthy. It is appreciated that caregiver medications might impact biomarkers. Thus medication use will be treated as a covariate in the analysis. We appreciate that eliminating subjects with illnesses requiring medications would skew the caregivers to only the very healthy and least likely to have health impairments associated with caregiving. Such a strategy would distort the potential impact of the intervention on biomarkers and behavior and weaken implications for caregivers in general. It is possible that objective caregiver burden might not change as a function of treatment since in many respects the time factors and financial burden do not change regardless of the intervention. However it is expected that the subject's perception of how stressful they present themselves (subjective burden) will change and this will be seen in affect and stress measures. In summary we remain very excited about this study as it will provide empirical evidence regarding the efficacy of the fPER intervention for caregivers of BMT patients. Further, it will provide behavioral and biomarker corroboration regarding the efficacy of fPER.

Data Safety And Monitoring Plan

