Data Aggregation, Distributional Assumptions, Missing Data/Attrition. Data will be screened for errors and outliers. Appropriate transformations will be made for non-normal outcomes. The pattern of participant dropout will be examined to ensure a reasonably equal distribution of participants lost to follow-up between groups. The analytic approach proposed uses maximum likelihood techniques that can include participants with incomplete data without need for imputation. These techniques are robust under certain conditions such that group comparisons will not be biased as long as missing data is ignorable.^{132,133} If this is not sufficient to minimize influences of particular observations, a sensitivity analysis will be conducted to help determine effects of missing data. Separate analyses of only those participants who complete the study will be conducted.

Verification of Randomization and Inclusion of Covariates. Preliminary analyses will validate that there are no baseline differences between intervention groups. We expect baseline differences will be accounted for by randomization, but should differences remain we will co-vary variables that are both correlated with the outcome and that differ by group.

Analytic Strategy In general, outcomes will be analyzed with linear mixed models comparing intervention (**fPER**, TAU) in patients and caregivers separately. An alpha level of 0.05 will be used to evaluate significance of the a priori planned comparisons. Two-tailed tests are proposed in order to detect differences between **fPER** and TAU in either direction. The software SAS PROC MIXED will be used.¹³⁴ The analytic aims and hypotheses are briefly stated, followed by overall analytic plan for primary and secondary outcomes:

Aim 2: Assess patient QOL following an allogeneic HSCT by the FACT-BMT as the primary patient outcome. Patients whose caregivers receive fPER will have improvements in FACT-BMT compared to TAU.

Aim 3: Test impact of fPER on caregiver composite distress score of depression, anxiety, and stress as the primary caregiver outcome. Caregivers who receive fPER will have reduced distress compared to TAU.

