For hypotheses addressing group differences for patients and separately for caregivers, outcomes will be evaluated with the same design: 2 groups (**fPER**, TAU) at 2 clinics (CBCI, UCH) over 4 times (prior to transplant, 6 wks., 3 mo., 6 mo.). Mixed models will specify group, clinic, time, and their interactions as fixed effects and subject as a random effect, where subject is assumed independently normally distributed with mean 0 and variance independent of the random errors. The primary caregiver model of composite distress will include caregiver age as a covariate because it related to caregiver distress in our prior study¹¹; secondarily, we will investigate inclusion of patient FACT-BMT as a covariate. The primary patient model of FACT-BMT will include no covariates, but secondarily will explore inclusion of caregiver distress as a covariate.

Aim 4: Assess biomarkers of allostatic load in patients prior to transplant and caregivers during the transplant process using novel biomarkers. Patient's hair cortisol will predict their QOL and distress at the beginning of the transplant process. fPER will be associated with reduced allostatic load in caregivers who receive fPER compared to those receiving TAU.

Linear mixed models will similarly be used to evaluate group differences in these biomarkers separately in patients and caregivers. Caregiver age and patient FACT-BMT will be evaluated for inclusion in caregiver models. Caregiver composite distress score will be evaluated for inclusion as a covariate in patient models.

Subject sample size and power analysis. Our prior trial demonstrated medium effect sizes (0.39-0.45) for PEPRR in caregivers. We believe the proposed modifications in **fPER** will likely increase its effect for caregivers. However, the effect of **fPER** on

Table 2. Minimum detectable effect sizes with specified sample size and power

Sample Size Per Group	80% Power	85% Power	90% Power	95% Power
112 Dyads	0.19	0.20	0.22	0.24
74 Dyads	0.23	0.25	0.27	0.30
62 Dyads	0.25	0.27	0.29	0.32

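### The primary FACT-BMT model lets each group have its own pre-randomisation mean and names no contrast for Aim 2, and the missing-data rules conflict

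*Combined protocol and SAP*

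**What the plan says.** Section IV.F, Analytic Strategy, sets one design for patients and caregivers: two groups "at 2 clinics (CBCI, UCH) over 4 times (prior to transplant, 6 wks., 3 mo., 6 mo". The model terms are: "Mixed models will specify group, clinic, time, and their interactions as fixed effects and subject as a random effect". For the primary patient outcome it adds: "The primary patient model of FACT-BMT will include no covariates".

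Section IV.C (fPER) fixes the timing of the first score: "Behavioral assessments will be collected prior to randomization, and at 6 weeks, 3 months and 6 months after transplant".

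Aim 2 is worded only as: "Patients whose caregivers receive fPER will have improvements in FACT-BMT compared to TAU". The same section sets two-sided 0.05 for a priori comparisons but does not list them.

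On missing data, IV.E says "we use intent to treat design with the last valid measure carried forward", while the first paragraph of IV.F says "The analytic approach proposed uses maximum likelihood techniques that can include participants with incomplete data without need for imputation".

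The paragraph in IV.F on verifying randomisation lets variables that differ by group and correlate with the outcome enter as covariates. It does not say whether this applies to the primary patient model.

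**The concern.** Randomisation makes the true group difference at the first visit zero. A group-by-time model with a separate baseline mean in each group spends information estimating that zero. The baseline score is already collected, so the lost precision could be recovered at no cost. The plan expects a smaller effect in patients than in caregivers, and heavy loss to follow-up, so precision matters.

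The unnamed contrast is the second problem. Improvement could mean the 3-month or 6-month difference, the change to either visit, the average of the follow-up visits, the group main effect, or the group-by-time interaction. These ask different questions and have different power. If none is named, the choice can be made after the results are known.

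The third is that two missing-data rules stand side by side. One of them would enter pre-randomisation scores as follow-up values.

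**Working it through.** **Inputs from the documents.** 112 dyads per arm, and losses of 34% at 3 months and 45% at 6 months taken from the prior caregiver trial (IV.F, sample size and power). Two-sided alpha 0.05. Random subject effect, hence equal within-patient correlation. Clinics of 150 and 75 dyads.

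**Assumed.** Within-patient correlation ρ of 0.3 to 0.7; 17% loss at 6 weeks (range 0-34%); monotone dropout; likelihood analysis as in IV.F; outcome in SD units; normal approximation.

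**Method.** The last visit attended is baseline, 6 weeks, 3 months or 6 months for shares 0.17, 0.17, 0.11 and 0.55. Information per arm is the sum over these patterns of 112 × share × the inverse correlation matrix of the visits seen. V, twice the inverse of that sum, is the variance matrix of the four group differences.
- Raw contrast: the follow-up difference, SE from V.
- Change contrast: follow-up minus baseline difference, SE from V.
- Common baseline: V of the follow-up differences, conditional on a zero baseline difference.

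**Hand check with complete data.** The raw SE is √(2/112) = 0.1336. The common-baseline SE is 0.1336 × √(1 − ρ²), which at ρ = 0.5 is 0.1157, or 13.4% lower. The change SE is 0.1336 × √(2(1 − ρ)), which equals the raw SE at ρ = 0.5. Below 0.5 raw is the better contrast; above it, change is.

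**SE reduction with the losses above, against the better of raw and change:**

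| ρ | Better contrast | 6 months | 3 months | Follow-up mean |
|---|---|---|---|---|
| 0.3 | raw | 2.7% | 3.1% | 6.4% |
| 0.4 | raw | 5.0% | 5.8% | 10.8% |
| 0.5 | equal | 8.4% | 9.7% | 16.4% |
| 0.6 | change | 6.6% | 7.5% | 12.6% |
| 0.7 | change | 4.8% | 5.5% | 9.2% |

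At ρ = 0.5 the SE falls from 0.1664 to 0.1524 (6 months), 0.1559 to 0.1408 (3 months) and 0.1218 to 0.1018 (follow-up mean). With the 6-week loss varied over 0-34%, the 6-month reduction stays at 8.3-8.5% and that of the mean at 15.0-17.5%.

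**Power at an illustrative 0.39 SD, ρ = 0.5**, from Φ(0.39/SE − 1.96):
- 6 months: 0.39/0.1664 = 2.34, 65%; 0.39/0.1524 = 2.56, 73%.
- 3 months: 0.39/0.1559 = 2.50, 71%; 0.39/0.1408 = 2.77, 79%.
- Follow-up mean, constant effect: 0.39/0.1218 = 3.20, 89%; 0.39/0.1018 = 3.83, 97%.
- Four-visit main effect: the effect becomes (0 + 3 × 0.39)/4 = 0.2925 with SE 0.1132, so 73%.

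The 0.39 is the prior trial's 3-month effect on caregiver perceived stress, so it is optimistic for patients.

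**Timing.** If the effect is late (0, 0.20, 0.39 SD at the three follow-ups), the average is 0.59/3 = 0.197 SD. The common-baseline mean then has 49% power, against 73% for the 6-month contrast. If it builds (0.13, 0.26, 0.39), they have 72% and 73%.

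**Carry-forward.** With 17% lost before 6 weeks, 17% of the 6-month values would be pre-randomisation scores. A constant 0.39 SD effect becomes 0.83 × 0.39 = 0.32 SD. For a 6-week loss of 34% to 0% the result is 0.26 to 0.39 SD.

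**Clinic weights.** Equal rather than size-proportional weights multiply the SE by √(0.25 × (1/75 + 1/150) × 225) = √1.125 = 1.061.

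**The case against.** The strongest reply is that the model is not wrong. A mixed model with baseline as a response gives valid follow-up and change contrasts, so the common baseline mean is a refinement. That stands. A reader might infer that the planned analysis is biased or invalid; nothing in the documents supports that, because baseline precedes randomisation and either contrast estimates a proper group difference.

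The size can also be overstated. A reader might take the ρ = 0.5 figures as typical, but 0.5 is where the gain over the better existing contrast peaks. Gains against the worse contrast are larger (31.9% for the follow-up mean against raw at ρ = 0.7), but there the plan's own change contrast leaves only 9.2%. Since no contrast is named, the larger figure cannot be charged to the plan.

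The power figures rest on a caregiver effect. The plan links FACT-BMT to the 0.19-0.20 in its effect-size table, whose metric is undefined: (1.96 + 0.84) × √(2/112) = 0.374, and half of that, 0.187, matches the printed 0.19. If 0.20 is in SD units, 6-month power is about 23%, rising only to about 26%; if the table is on a half scale, 0.39 SD is about right. The powers are therefore illustrations.

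Finally, the covariate rule might be thought to supply baseline adjustment. It acts only when an observed difference appears, and the specific statement of no covariates may override it.

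**Conclusion.** The point holds as a matter of precision and specification. Two textual findings need no assumption: no term or visit is named for Aim 2, and the two missing-data rules disagree. Using the main effect over all four visits would cost a quarter of a constant effect.

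The precision gain was positive in every case computed, and it is modest at a single visit: about 3-8% at 6 months, 3-10% at 3 months and 6-16% for the follow-up mean, against the better existing contrast. These figures depend on an assumed correlation of 0.3-0.7 and an assumed 6-week loss, neither of which the documents give, and on the likelihood analysis in IV.F. The carry-forward shrinkage applies to the extent that patients are lost before 6 weeks, a rate the documents do not state. The change should be made, but the trial's validity does not hinge on the common baseline.

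**What to change.** Before unblinded data are seen:

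1. Keep all four visits as responses, but constrain the two groups to a common baseline mean within each clinic, since the model has clinic interactions. Use an unstructured within-subject covariance and Kenward-Roger degrees of freedom. Dyads with only a baseline score stay in the model.
2. Name one primary follow-up contrast, either a specific visit or the post-transplant average, and its clinic weights. The sponsor should choose it on the expected timing of the effect; the schedule is relevant, with five of ten sessions by week 6 and the programme extended "to include two additional sessions between 4-6 months post-transplant". Report the other visits as supportive.
3. State that the maximum-likelihood analysis in IV.F governs, and delete the carry-forward rule in IV.E.
4. State that observed baseline differences do not add covariates to the primary model.
5. Use the same form for caregiver distress, keeping age.

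The cost is wording only, with no new data. The unstructured covariance has 10 parameters instead of 2, a small cost not included in the figures above. A follow-up average loses power if the effect is late.

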Allogeneic hematopoietic stem cell transplant (HSCT) caregivers must be available 24/7 for the first 100 days and often longer following a transplant. However behaviorally and more importantly medically healthy caregivers are essential for the best patient outcome. Few interventions for caregivers have been tested by randomized clinical trials (RCT). Our objective is to determine if a stress management intervention for allogeneic HSCT caregivers compared to self-care relying on resources of the transplant program (treatment as usual, TAU) would be associated with lower stress. We designed a randomized control trial with intent-to-treat of an eight session manualized stress management intervention provided to caregivers following transplant. Subjective behavioral data collected longitudinally for 12 months using standardized instruments was entered blindly. The HSCT caregivers were recruited from a community transplant program between November 2008 and April 2012. The study included a consecutively approached sample of 267 caregivers of allogeneic HSCT patients. 148 (mean age=53.5 years, 75.7% female) were randomized to a manualized intervention (n=74) or TAU (n=74). 101 caregivers reached the three month follow-up with drop outs associated with patient and/or caregiver factors. The intervention included an eight session stress management program provided to caregivers by a social worker during the immediate post-transplant period that focused on learning about stress, changing role(s) of the caregiver, cognitive behavioral approach to managing stress, paced respiration with a commercial biofeedback device, and identifying resources. A panel of questionnaires and physiological markers was collected from the caregivers five times over the course of one year beginning in the peri-transplant period. The primary outcome measure was self-reported perceived stress. Secondary outcome measures included depression, anxiety, caregiver burden, physical health, sleep, trauma and composite scores of these measures. Groups did not differ at baseline. Controlling for age, the intervention resulted in significantly lower ($p=0.039$) caregiver perceived stress (primary outcome) at 3 months post-transplant (Mean=20.0, SD=1.0) compared to TAU (Mean=23.0, SD=1.0) with an effect size (ES) of 0.39. The intervention group showed significantly better ($p=0.019$) scores on a secondary composite score that includes depression, anxiety, and other distress measures (Mean=-0.22, SD=0.13) compared to TAU (Mean=0.23, SD=0.13) with an ES of 0.45. This study had limitations due to problems with low minority subject recruitment, logistics of collecting dependent measures when patients and caregivers moved out of the area, as well as missing data. While needing further study within more settings, this approach is likely to improve caregiver well-being and potentially that of patients.

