patient QOL is indirect, and thus smaller effect sizes would be expected. We estimated minimum effect sizes detectable for different power specifications for a recruited sample size of 112 per treatment group and also for smaller sample sizes, allowing for increased variability due to estimated losses to follow-up of 34% at 3 mo., and 45% at 6 mo. based on our prior caregiver trial. Estimates are conservative since **fPER** has been specifically modified to reduce attrition. 112 dyads (consisting of a caregiver and patient) randomized to each group provide excellent power (>95%) for detecting the medium effect size expected for the composite distress score in caregivers and are necessary to provide adequate power (80-85%) for detecting smaller effect sizes expected for the FACT-BMT QOL measure in patients. Estimates are also conservative because mixed model analyses that include all subjects (even those with only a single observation) have been shown to provide the greatest power.¹²⁷

G. Summarize Knowledge to be Gained:

This study will provide empirical evidence regarding both behavioral and possible physiological efficacy of a stress management psychoeducation program for caregivers and the impact on patient QOL. This is one of the few studies of its kind that promises to provide not only information regarding behavioral outcome for the patients as far as quality of life but also impact their caregivers. The results of this study will lead to the availability of a manual developed for this intervention that can be disseminated to other HSCT programs leading to improved patient QOL and reduced caregiver distress.

H. References:

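### The power table names no effect-size metric and its entries are half of SD units, so it does not support the stated power for caregivers (>95%) or FACT-BMT (80-85%)

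*Combined protocol and SAP*

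**What the plan says.** Section IV.F, under the sample-size and power heading, starts from the earlier trial: "Our prior trial demonstrated medium effect sizes (0.39-0.45) for PEPRR in caregivers". It adds that the changes made for fPER "will likely increase its effect for caregivers", without giving a larger value, and that the effect on patient quality of life should be smaller because it is indirect. The table that follows is captioned "Table 2. Minimum detectable effect sizes with specified sample size and power". It has rows for 112, 74 and 62 dyads per group and names no metric, SD, contrast or within-subject correlation. For 112 dyads the entries are 0.19, 0.20, 0.22 and 0.24 at 80%, 85%, 90% and 95% power.

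From this the plan draws two conclusions about 112 dyads per group. On the caregiver outcome, it says that they "provide excellent power (>95%) for detecting the medium effect size expected for the composite distress score in caregivers". On the patient outcome, for which it gives no expected FACT-BMT effect, it says that these numbers "are necessary to provide adequate power (80-85%) for detecting smaller effect sizes expected for the FACT-BMT QOL measure in patients". The section then describes the estimates as conservative, because mixed models that use all subjects have more power.

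**The concern.** A reader will take the table's 0.19-0.24 and the prior effects of 0.39-0.45 to be on one scale. On that reading the trial can detect an effect about half the size of the caregiver effect, which would suit an indirect effect on patients. If the table is in fact on a scale of half SD units, 0.19-0.20 is about the same size as the caregiver effect itself, and the margin disappears.

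The 80-85% figure is the stated reason why 112 dyads per group are needed for the trial's primary outcome. A reader who relies on the table could take a null FACT-BMT result as evidence against effects that the table does not show the trial can detect.

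**Working it through.** **Inputs.** Two-sided alpha 0.05 (IV.F, Analytic Strategy); 112 per group; losses of 34% at 3 months and 45% at 6 months (IV.F, sample size). The lower rows follow from these: 112 × 0.66 = 73.9, so 74; 112 × 0.55 = 61.6, so 62.

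**1. Reproducing the table.** For a two-group comparison of means, the detectable difference in SD units is d = (z₀.₉₇₅ + z_power) × √(2/n). For n = 112 and 80% power: (1.960 + 0.842) × √(2/112) = 0.374. Half of that is 0.187, printed as 0.19. The full set:

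| n per group | | 80% | 85% | 90% | 95% |
|---|---|---|---|---|---|
| 112 | d | 0.374 | 0.400 | 0.433 | 0.482 |
| | d/2 | 0.187 | 0.200 | 0.217 | 0.241 |
| | printed | 0.19 | 0.20 | 0.22 | 0.24 |
| 74 | d | 0.461 | 0.493 | 0.533 | 0.593 |
| | d/2 | 0.230 | 0.246 | 0.266 | 0.296 |
| | printed | 0.23 | 0.25 | 0.27 | 0.30 |
| 62 | d | 0.503 | 0.538 | 0.582 | 0.647 |
| | d/2 | 0.252 | 0.269 | 0.291 | 0.324 |
| | printed | 0.25 | 0.27 | 0.29 | 0.32 |

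All 12 cells match d/2 and none matches d. For two equal groups d/2 is Cohen's f. That the table is in f is an inference; the plan does not say so.

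**2. The scale of the prior effects.** Section III reports the composite as "Mean=-0.22, SD=0.13) compared to TAU (Mean=0.23, SD=0.13) with an ES of 0.45". The difference is 0.23 − (−0.22) = 0.45 and the effect size is 0.45, so the underlying SD is 1 and the effect is in SD units. Perceived stress is reported as "Mean=20.0, SD=1.0) compared to TAU (Mean=23.0, SD=1.0) with an effect size (ES) of 0.39": 3.0 / 0.39 = 7.7, the implied SD.

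The printed SDs of 0.13 and 1.0 behave as standard errors:
- As SDs they would give effects of 0.45/0.13 = 3.5 and 3.0/1.0 = 3.0.
- As standard errors they give z = 0.45/(0.13√2) = 2.45, p = 0.014 (stated 0.019), and z = 3.0/(1.0√2) = 2.12, p = 0.034 (stated 0.039).
- The caption of Figure 5 labels its age-adjusted means as shown with SEM.
- With the effects read as d, the implied number per arm is (1/0.13)² = 59 for the composite and (7.7/1.0)² = 59 for perceived stress. This fits 74 randomized per arm, of whom "101 caregivers reached the three month follow-up" in total. Read as f, the implied number is about 15 per arm, which does not fit.

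**3. Power in matching units.** Power ≈ Φ(d√(n/2) − 1.96), the calculation that reproduces the table:

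| n per group | 0.20 SD | 0.39 SD | 0.45 SD | d for 95% |
|---|---|---|---|---|
| 112 | 32% | 83% | 92% | 0.48 |
| 74 | 23% | 66% | 78% | 0.59 |
| 62 | 20% | 58% | 71% | 0.65 |

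The t distribution lowers these powers by less than one percentage point.

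**4. What the 80% and 85% columns mean for FACT-BMT.** They mean 0.37-0.40 SD at 112 per group, 0.46-0.49 at 74 and 0.50-0.54 at 62. For 80% power at 0.20 SD, the same calculation needs 2 × (1.960 + 0.842)² / 0.20² ≈ 393 per group.

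**5. What the planned mixed model could add.** The assumptions here are mine: compound symmetry, 112 per group, four visits, 85% retention at 6 weeks, then the stated losses, equal baseline means, and the average of the three follow-up visits as the contrast.

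| Within-subject correlation | Detectable effect at 80% power |
|---|---|
| 0.50 | 0.28 SD |
| 0.67 | 0.25 SD |
| 0.81 | 0.20 SD |
| 0.86 | 0.18 SD |

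At correlations of 0.50-0.67, power is 97-99% for 0.39 SD and over 99% for 0.45 SD.

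Detecting 0.20 SD with 80% power needs a correlation of about 0.81. It is 0.79-0.84 if 6-week retention is 100% down to 70%, and 0.73 with no losses at all. It rises to about 0.84 for average change from baseline, and to about 0.90 and 0.91 for the 3-month or 6-month visit alone.

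**The case against.** The strongest reply has four parts.

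- **The caregiver claim is not tied to 0.39-0.45.** The plan expects fPER to do better than its predecessor. Only 0.48 SD is needed for 95% power at full retention, and 0.50 SD gives 96%. This is fair, but no expected value is printed, and 0.39-0.45 is the range the plan itself calls medium.
- **The new composite may be stronger.** It keeps three measures whose prior effects were 0.39, 0.46 and 0.66 (IV.D). An equal-weight composite has effect (0.39 + 0.46 + 0.66)/√(3 + 6r). With an assumed inter-measure correlation r of 0.8-0.6 that is 0.54-0.59 SD, with 98-99% power at 112 per group, 91-95% at 74 and 85-91% at 62. The plan states no such effect, however, and the five-measure composite gave 0.45.
- **The analysis is a four-visit mixed model, not a single-visit test.** At moderate correlation this supports the caregiver figure on an averaged contrast, as step 5 shows. But the plan presents the mixed-model gain as a further margin, not as part of the table, and names no contrast or correlation. It gives no within-patient correlation for FACT-BMT over follow-up, only a reliability of .86 of unspecified type. Other instruments range from .51-.67 (CES-D) to .9 (CRA). Neither end can be excluded.
- **A factor of one half could arise in other ways**, for example from baseline adjustment at a correlation near 0.87. Nothing in the plan says so.

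What stands is that the true power may be adequate, particularly for caregivers. The table does not show it.

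**Conclusion.** The concern holds. The table is arithmetically sound on a half-SD scale, but it is set without a label beside effects in SD units. On its own calculation, 112 per group gives 83-92% power for the cited caregiver effects, and 58-78% at the expected retained numbers, not more than 95%. The 80-85% columns correspond to 0.37-0.40 SD with no loss and 0.46-0.54 SD with the stated losses. They therefore do not support 80-85% power for patient effects expected to be smaller than the caregiver effect.

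This rests on the plain two-group reading that reproduces every cell, and on the prior effects being in SD units, which the preliminary results bear out. The claim is that the stated power is unsupported, not that it is too high under every contrast and correlation. It must be corrected because the patient figure is the stated justification of the sample size for the primary outcome.

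**What to change.** 1. Name the effect-size metric in the table.
2. Either restate the table in SD units (the d rows in step 1), or recompute it for a named primary contrast with a stated within-subject correlation and the stated losses.
3. Replace both power statements with values for a stated SD-unit effect, at the recruited and at the expected retained sample size.
4. State the detectable FACT-BMT effect in SD units.
5. In passing, correct the citation behind the remark on mixed-model power: reference 127 is a hair-cortisol heritability study. The remark itself may stay.

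The cost is one table and a few sentences. Enrolment need not change. The stated power becomes less favourable unless the sponsor names a contrast and correlation that support it.
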